### 5.2. SAMPLE SIZE

This observational study will include all eligible infants enrolled at UAB RNICU and NBN.

#### **Aim 1 (Comparison of lung compliance in term and pre-term infants)**

Assuming lung reactance at 7 Hz ( $X_7$ ) initial measurements will have an absolute 20% difference (more negative) in preterm infants without RDS compared to term controls will need to recruit 264 infants (132 term and 132 preterm infants) assuming power of 90%, type I error rate of 5% and standard deviation of 0.5 of the mean.

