### 5.1. STATISTICAL ANALYSIS PLAN

Results will be analyzed by the Student's t test, as appropriate for parametric data, and by Mann-Whitney U rank sum test for nonparametric data. A  $p$  value of  $<0.05$  will be considered statistically significant.

Non-independent parametric data will be analyzed by the paired Student's t test, and Wilcoxon signed rank test for non-independent non-parametric data.

Chi-square or Fisher's exact test will be used as appropriate to analyze categorical data.

Analysis of covariance and multiple regression models will be used to examine the interaction between, and the independent effects of factors including birth weight, gestational age, gender, ethnicity, socioeconomic group, maternal smoking, type and severity of lung disease, treatment with surfactant (including number of doses), days of mechanical ventilation before study entry, days of respiratory support before study entry, treatment with antenatal steroids, and treatment with postnatal steroids upon primary and secondary outcomes.

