#### **Aim 2 (Comparison of BPD and non-BPD lung compliance)**

Assuming lung reactance at 7 Hz ( $X_7$ ) initial measurements will have an absolute 20% difference (more negative initially) in preterm infants with RDS who go on to develop BPD (including O2 requirement at 28 days –mild BPD) compared to preterm controls with RDS who do not develop BPD will need to recruit 264 infants (132 BPD, 132 non-BPD) assuming power of 90%, type I error rate of 5% and standard deviation of 0.5 of the mean.

It will not be possible to know in advance which infants with RDS will go on to develop BPD so we plan to enroll as many preterm infants with RDS as possible until the sample size for infants with RDS who develop BPD is reached.

Aim 2 (

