#### **Aim 3 (Comparison of common neonatal respiratory disorders)**

RDS - Assuming lung reactance at 7 Hz ( $X_7$ ) initial measurements will have an absolute 20% difference (more negative) in preterm infants with RDS compared to preterm controls will need

to recruit 264 infants (132 per arm) assuming power of 90%, type I error rate of 5% and standard deviation of 0.5.

BPD - Assuming lung reactance at 7 Hz ( $X_7$ ) initial measurements will have an absolute 20% difference (more negative) in preterm infants with BPD compared to preterm controls will need to recruit 264 infants (132 per arm) assuming power of 90%, type I error rate of 5% and standard deviation of 0.5 of the mean.

TTN - Assuming lung reactance at 5 Hz ( $X_5$ ) initial measurements will have an absolute 20% difference (more negative) in term infants with TTN compared to term controls will need to recruit 264 infants (132 per arm) assuming power of 90%, type I error rate of 5% and standard deviation of 0.5 of the mean.

MAS - Assuming lung reactance at 7 Hz ( $X_7$ ) initial measurements will have an absolute 50% difference (more negative) in term infants with MAS compared to term controls will need to recruit 42 infants (21 per arm) assuming power of 90%, type I error rate of 5% and standard deviation of 0.5 of the mean.

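### Section 5.1 names only the pooled-variance Student's t test for parametric two-group comparisons, although Aim 2 and MAS are likely to have unequal arms; Welch's test would protect the error rate at almost no cost

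*Combined protocol and SAP*

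**What the plan says.** For independent groups, section 5.1 states: "Results will be analyzed by the Student's t test, as appropriate for parametric data". The Mann-Whitney test is named for nonparametric data. No unequal-variance t test is mentioned.

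Section 5.2, Aim 1, sizes a 20% difference at 132 per group, "assuming power of 90%, type I error rate of 5% and standard deviation of 0.5 of the mean". Aim 2 and the Aim 3 lines for BPD, TTN and MAS use the same SD phrase. The Aim 3 RDS line gives the SD as 0.5 with no reference to a mean. In every line the case mean is assumed to be more negative than the control mean: by 20%, or by 50% for MAS. The MAS line reads "compared to term controls will need to recruit 42 infants (21 per arm) assuming power of 90" per cent.

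Three statements bear on the arm sizes:

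- Section 5.2, Aim 2, plans to "enroll as many preterm infants with RDS as possible until the sample size for infants with RDS who develop BPD is reached". The number without BPD is therefore not fixed.
- Section 4.2.4, Aim 3 control, makes term infants without lung disease the controls for term infants with lung disease, and sets no limit of 21.
- Section 5.2 opens by including all eligible enrolled infants. Aim 1 alone calls for 132 term infants without lung disease.

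**The concern.** Student's t test estimates one variance from both groups. With equal arms this does little harm even if the variances differ. With unequal arms the larger group dominates the pooled estimate. If the smaller group is the more variable one, the standard error is too small, p values are too low and confidence intervals too narrow.

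The plan could produce this pattern in two comparisons. The BPD and MAS groups have the more negative assumed mean, and they are the groups likely to be outnumbered. If the spread of reactance rises with its magnitude, which is one way to read an SD quoted as a fraction of the mean, they are also the more variable. A reported BPD or MAS difference would then carry more than the declared 5% error.

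**Working it through.** **Inputs.** From section 5.2: differences of 0.20 and 0.50 of the control mean, SD 0.5, alpha 5%, power 90%, 132 and 21 per arm. Two-sided testing is not stated; it is assumed because it reproduces the sizes (one-sided gives 108 and 18). Assumptions of this check: SD = 0.5 × each group's own mean, so controls 0.50, a group 20% more negative 0.60, MAS 0.75; non-BPD counts of 264 and 396 as illustrations; all 132 term controls used for MAS.

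**The plan's own sizes.** With one common SD of 0.5 of the control mean, n per arm = 2(1.96 + 1.2816)² × (SD/difference)².

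- 20%: 2 × 3.2416² × (0.5/0.2)² = 131.3, so 132.
- 50%: 2 × 3.2416² × 1 = 21.01, stated as 21.

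Both reproduce; power by the normal approximation is 90.1% and 90.0%.

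**Error rate of Student's t.** Compare the standard error that the test uses with the true one:

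- pooled variance = [(n₁ − 1)s₁² + (n₂ − 1)s₂²]/(n₁ + n₂ − 2)
- pooled SE = √[pooled variance × (1/n₁ + 1/n₂)]
- true SE = √(s₁²/n₁ + s₂²/n₂)
- error rate ≈ 2[1 − Φ(t critical × pooled SE/true SE)]

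*Aim 2, 132 v 264.* Pooled variance = (131 × 0.36 + 263 × 0.25)/394 = 0.2866. Pooled SE = 0.0571; true SE = √(0.36/132 + 0.25/264) = 0.0606; ratio 0.941. Effective critical value 1.966 × 0.941 = 1.85, so the error rate is 6.4% (simulated 6.5%; Welch 5.0%).

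*Aim 2, 132 v 396.* Pooled SE = 0.0529; true SE = 0.0580; ratio 0.913. Effective critical value 1.79, error rate 7.3% (simulated 7.3%; Welch about 5%).

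*MAS, 21 v 132.* Pooled variance = (20 × 0.5625 + 131 × 0.25)/151 = 0.2914. Pooled SE = 0.127; true SE = √(0.5625/21 + 0.25/132) = 0.169; ratio 0.749. Effective critical value 1.976 × 0.749 = 1.48, error rate 13.9% (simulated 14%; Welch about 5%).

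*Equal arms.* The two standard errors coincide. Simulated error for Student's t is 5.0% at 132 per arm and 5.1% at 21 per arm.

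**Price of Welch if variances are equal.** At 21 v 132 with SD 0.5 in both groups and a 50% difference, simulated power is about 98.3% for Welch and 98.8% for Student's t.

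**Sensitivity of power to the SD reading (Welch, noncentral t).**

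- 132 v 132, 20%: SE = √[(0.25 + 0.36)/132] = 0.0680; 0.2/0.0680 = 2.94; power 83%.
- Aim 2 at 132 v 264: 0.2/0.0606 = 3.30; power about 91%.
- MAS 21 v 21: SE = √[(0.25 + 0.5625)/21] = 0.197; 0.5/0.197 = 2.54; power about 70%.
- MAS 21 v 132: 0.5/0.169 = 2.95; power 81%.

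**The case against.** A reader might infer that the stated 90% power is an error and that the true figures are 83% and 70%. The documents do not support that. The stated sizes reproduce with one common SD, and each comparison quotes a single SD. The RDS line says only 0.5. The within-infant comparisons of Aim 4 also fit one fixed SD: 3.2416² × (0.5/d)² gives 116.7, 65.7 and 29.2 for d = 0.15, 0.20 and 0.30, against planned totals of 120, 70 and 30. The lower figures rest on a reading that the plan does not state. Even on that reading, Aim 2 regains its power once surplus non-BPD infants are enrolled.

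A reader might also infer that Student's t is unsuitable throughout. It is not: with the 1:1 arms used for sizing, it holds its level and has essentially the same power as Welch. Nor does the plan limit MAS to 21 controls. Sections 4.2.4 and 5.2 already allow all term controls, and it is this permission that makes the MAS arms unequal.

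The error rates are conditional in a further way. They are computed at equal means with the SDs held at the stated values. If the SD were strictly proportional to the mean, the SDs would be equal when the means are equal. The same percentages then describe how often a nominal 95% interval misses the planned difference: coverage of about 93% to 94% in Aim 2 and 86% in MAS.

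Finally, section 5.1 qualifies Student's t with a suitability condition and offers the Mann-Whitney test. That choice depends on whether data are parametric. It does not name a method for parametric data with unequal spread.

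**Conclusion.** The point holds for the choice of test. Section 5.1 provides only a pooled-variance test for parametric two-group data, while the plan's recruitment and control rules make unequal arms likely in Aim 2 and possible in MAS. If the case groups are more variable in proportion to their assumed means, the nominal 5% becomes about 6.4% to 7.3% in Aim 2 and about 14% in MAS. The Aim 2 excess is modest and depends on the assumed non-BPD counts. The MAS figure depends on using all 132 term controls. If the SDs are equal, or the arms are equal, there is no inflation.

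The power statement is a matter of clarity only. The 90% is right for a common SD. If 0.5 is a coefficient of variation in each group, power would be about 83% for the 1:1 comparisons of 20% whose text ties the SD to the mean: Aim 1, BPD, TTN, and Aim 2 only if it stays at 132 v 132. For MAS it would be about 70% at 21 v 21.

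**What to change.** In section 5.1, replace Student's t test with Welch's t test for the independent two-group comparisons, with confidence intervals from the same method. The paired tests are not affected.

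In section 5.2, say whether 0.5 is a common SD based on the control mean or a coefficient of variation in each group. If it is the former, the stated 90% stands. If it is the latter, give the power on that basis for the arm sizes expected, including about 91% for Aim 2 at 132 v 264 and about 81% for MAS at 21 v 132.

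Both are wording changes. They need no extra infants or measurements, and the loss of power if variances prove equal is about half a percentage point at 21 v 132.

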#### **Aim 2 (Comparison of BPD and non-BPD lung compliance)**

Assuming lung reactance at 7 Hz ( $X_7$ ) initial measurements will have an absolute 20% difference (more negative initially) in preterm infants with RDS who go on to develop BPD (including O2 requirement at 28 days –mild BPD) compared to preterm controls with RDS who do not develop BPD will need to recruit 264 infants (132 BPD, 132 non-BPD) assuming power of 90%, type I error rate of 5% and standard deviation of 0.5 of the mean.

It will not be possible to know in advance which infants with RDS will go on to develop BPD so we plan to enroll as many preterm infants with RDS as possible until the sample size for infants with RDS who develop BPD is reached.

Aim 2 (

#### **Aim 3 (Comparison of common neonatal respiratory disorders)**

RDS - Assuming lung reactance at 7 Hz ( $X_7$ ) initial measurements will have an absolute 20% difference (more negative) in preterm infants with RDS compared to preterm controls will need

to recruit 264 infants (132 per arm) assuming power of 90%, type I error rate of 5% and standard deviation of 0.5.

BPD - Assuming lung reactance at 7 Hz ( $X_7$ ) initial measurements will have an absolute 20% difference (more negative) in preterm infants with BPD compared to preterm controls will need to recruit 264 infants (132 per arm) assuming power of 90%, type I error rate of 5% and standard deviation of 0.5 of the mean.

TTN - Assuming lung reactance at 5 Hz ( $X_5$ ) initial measurements will have an absolute 20% difference (more negative) in term infants with TTN compared to term controls will need to recruit 264 infants (132 per arm) assuming power of 90%, type I error rate of 5% and standard deviation of 0.5 of the mean.

MAS - Assuming lung reactance at 7 Hz ( $X_7$ ) initial measurements will have an absolute 50% difference (more negative) in term infants with MAS compared to term controls will need to recruit 42 infants (21 per arm) assuming power of 90%, type I error rate of 5% and standard deviation of 0.5 of the mean.

#### **Aim 4 (Comparison of lung compliance response to therapeutic intervention)**

Methylxanthines - Assuming lung reactance at 7 Hz ( $X_7$ ) measurements will have an absolute 15% difference (more positive) lung compliance following this therapy we plan to recruit 120 infants (60 per arm) assuming power of 90%, type I error rate of 5% and standard deviation of 0.5 of the mean.

Physical therapy - Assuming lung reactance at 7 Hz ( $X_7$ ) measurements will have no significant difference with a non-inferiority margin of 15% following this therapy we plan to recruit 120 (60 per arm) infants assuming power of 90%, type I error rate of 5% and standard deviation of 0.5 of the mean.

Nebulized cromolyn sodium - Assuming lung reactance at 7 Hz ( $X_7$ ) measurements will have no significant difference with a non-inferiority margin of 15% following this therapy we plan to recruit 120 infants (60 per arm) assuming power of 80%, type I error rate of 5% and standard deviation of 0.5 of the mean.

Albuterol - Assuming lung reactance at 7 Hz ( $X_7$ ) measurements will have an absolute 15% difference (more positive) following this therapy we plan to recruit 120 infants assuming power of 90%, type I error rate of 5% and standard deviation of 0.5 of the mean.

Furosemide - Assuming lung reactance at 7 Hz ( $X_7$ ) measurements will have an absolute 20% difference (more positive) following this therapy we plan to recruit 70 infants assuming power of 90%, type I error rate of 5% and standard deviation of 0.5 of the mean.

Chlorothiazide - Assuming lung reactance at 7 Hz ( $X_7$ ) measurements will have an absolute 20% difference (more positive) following this therapy we plan to recruit 70 infants assuming power of 90%, type I error rate of 5% and standard deviation of 0.5 of the mean.

Systemic postnatal steroids for BPD - Assuming lung reactance at 7 Hz ( $X_7$ ) measurements will have an absolute 30% difference (more positive) following this therapy, we plan to recruit 30 infants assuming power of 90%, type I error rate of 5% and standard deviation of 0.5 of the mean.

Inhaled postnatal steroids for BPD - Assuming lung reactance at 7 Hz ( $X_7$ ) measurements will have an absolute 30% difference (more positive) following this therapy we plan to recruit 30

infants assuming power of 90%, type I error rate of 5% and standard deviation of 0.5 of the mean.

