#### **4.2.4. Control or Monitoring of Co-interventions**

Aim 1 control: baseline oscillometry measurements will be compared over time between preterm infants and term infants without lung disease as defined by need for respiratory support.

Aim 2 control: preterm infants with RDS who go on to develop BPD will be compared with preterm infants with RDS who do not go on to develop BPD. Preterm infants who do not develop BPD will serve as controls for RDS infants who develop BPD.

Aim 3 control: baseline pulmonary function tests and serial changes over time will be compared between infants with and without lung disease. Preterm infants without lung disease will act as controls for preterm infants with lung disease. Term infants without lung disease will act as controls for term infants with lung disease.

Aim 4 control: The timing of pulmonary function testing among infants with lung disease will be recorded in relation to the timing of interventions, as ordered by the treating physician, which may affect pulmonary function including bronchodilators, steroids, diuretics, methylxanthines, different forms of physical therapy, and nebulized/inhaled medications, to determine the effects of these treatments on pulmonary function pairing the pre-treatment pulmonary function values (control) for an individual patient with the post-treatment values (intervention) for the same individual patient.

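### Aim 4 pairs each infant with itself, yet three therapy lines split 120 infants into two arms of 60, and physical therapy and cromolyn state 90% and 80% power from identical inputs

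*Combined protocol and SAP*

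**What the plan says.** Section 4.2.4 (Aim 4 control) defines the comparison as "pairing the pre-treatment pulmonary function values (control) for an individual patient with the post-treatment values (intervention) for the same individual patient". Section 5.1 fits that design: "Non-independent parametric data will be analyzed by the paired Student's t test", with the signed rank test as the nonparametric counterpart.

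The Aim 4 part of section 5.2 sizes eight therapies. Three of them are split into arms:

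- Methylxanthines, 15% change: "we plan to recruit 120 infants (60 per arm) assuming power of 90%, type I error rate of 5"%.
- Physical therapy, 15% margin: "we plan to recruit 120 (60 per arm) infants assuming power of 90%, type I error rate of 5"%.
- Nebulized cromolyn, 15% margin: "we plan to recruit 120 infants (60 per arm) assuming power of 80%, type I error rate of 5"%.

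The other five lines have no split. Albuterol has the same 15% change, power, error rate and SD as methylxanthines and reads "following this therapy we plan to recruit 120 infants assuming power of 90%, type I error rate of 5"%. Furosemide and chlorothiazide give 70 infants for 20%, and systemic and inhaled steroids give 30 for 30%. Every line uses an SD of half the mean.

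Physical therapy and cromolyn both assume "no significant difference with a non-inferiority margin of 15% following this therapy".

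**The concern.** There are two separate problems.

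First, a comparison of an infant with itself has no second arm. In the Aim 3 part of section 5.2, an arm is a separate group of infants (132 per arm for a 20% difference). Read that way in Aim 4, 60 per arm would mean that a smaller 15% difference, with the same SD, error rate and power, needs fewer infants per group than a 20% difference. That cannot be. A reader may also take 60 as the number of infants who need paired measurements, which would halve the target.

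Second, physical therapy and cromolyn have the same margin, sample size, error rate and SD but different powers. The wording mixes an absence of difference with a non-inferiority margin, and section 5.1 names neither a non-inferiority nor an equivalence test. What would count as success for these two therapies is therefore not fixed in advance. Two identically specified comparisons carry a 10% and a 20% chance of failing to show the planned result when there is no true difference.

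**Working it through.** **Inputs (section 5.2, Aim 4).** Change or margin δ = 0.15 of the mean, SD = 0.5 of the mean, error rate 5%, N = 120. The superiority lines are taken as two-sided. For the two margin lines the true difference is taken as 0.

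**Assumption.** The plan does not say whether 0.5 is the SD of the within-infant change or of a single measurement. Steps 1 to 3 take it as the SD of the change; step 4 varies this.

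**Step 1. Reproduce the plan's 120.** For a paired comparison, n = [SD × (z₀.₉₇₅ + z₀.₉₀) / δ]² = [0.5 × (1.960 + 1.282) / 0.15]² = 116.7, so 117 pairs, or 119 with the t distribution. At 120 pairs the noncentrality is 0.30 × √120 = 3.29 and the power is 90.3%. The stated 120 and 90% are reproduced as a count of pairs.

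The unsplit lines follow the same method:

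| Change | Stated N | Power if N pairs | Power if two groups of N/2 |
|---|---|---|---|
| 20% | 70 | 91.0% | 37.8% |
| 30% | 30 | 88.8% | 35.5% |

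**Step 2. Try the split for methylxanthines.**

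- 60 pairs: noncentrality 0.30 × √60 = 2.32, power 62.8%.
- Two independent groups of 60: noncentrality 0.30 × √(60/2) = 1.64, power 37.1%. Two independent groups would need 2 × 116.7 = 233.5, so 234 per group (235 with the t distribution), for 90%.

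Neither reading gives 90%.

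**Step 3. Physical therapy and cromolyn.** Normal-approximation formulas, with z at the per-side alpha:

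- Non-inferiority power = Φ(δ√n/SD − z).
- Equivalence power (two one-sided tests) = 2Φ(δ√n/SD − z) − 1.

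For example, equivalence at 2.5% per side with 120 pairs is 2Φ(3.286 − 1.960) − 1 = 81.5%; the exact t-based figure is 80.6%. The t-based results are:

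| Test and alpha | 120 pairs | 60 pairs |
|---|---|---|
| Non-inferiority, one-sided 2.5% | 90.3% | 62.8% |
| Non-inferiority, one-sided 5% | 94.8% | 74.3% |
| Equivalence, 5% per side | 89.5% | 48.6% |
| Equivalence, 2.5% per side | 80.6% | 25.8% |

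At 120 pairs, 90% matches either non-inferiority at 2.5% or equivalence at 5% per side. Only equivalence at 2.5% per side gives 80%. No single row gives both.

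**Step 4. If 0.5 is the SD of one measurement.** With equal SDs before and after treatment, SD of change = 0.5 × √[2(1 − ρ)], where ρ is the pre/post correlation. The documents give no value for ρ. Power for a 15% change, two-sided 5%:

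| ρ | SD of change | 120 pairs | 60 pairs |
|---|---|---|---|
| 0 | 0.707 | 63% | 37% |
| 0.25 | 0.612 | 76% | 46% |
| 0.3 | 0.592 | 79% | 49% |
| 0.5 | 0.500 | 90% | 63% |
| 0.7 | 0.387 | 99% | 84% |

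A total of 120 pairs reaches 90% at ρ of about 0.49; 60 pairs reach it only at about 0.75.

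**The case against.** The arm split can be called a slip of wording. The study is observational, treatment is by physician order, and section 5.2 opens with "This observational study will include all eligible infants enrolled at UAB RNICU and NBN", so no allocation depends on the split. All three lines say to recruit 120, and the word arm is used loosely elsewhere: Aim 3 applies it to disease and control cohorts. This stands. The 60-pair and 60-per-group powers show that the label does not fit; they do not forecast what the study will deliver.

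On power, 80% could be a minimum target, which 120 pairs exceed under either non-inferiority convention. On the plain non-inferiority reading at one-sided 2.5%, the physical therapy figure is right and the cromolyn figure is merely conservative. A typing slip is also possible. These explanations are plausible, but each leaves the cromolyn line misstated: 120 pairs do not correspond to 80% under non-inferiority, which would need 90 pairs at one-sided 2.5% or 71 at 5%. They also leave the test and its alpha unstated.

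The powers do rest on an SD that the plan does not define, and any range for the correlation is the reader's choice. That limits how firmly any single power can be stated. It does not touch either contradiction: a paired comparison has no arms, and identical inputs under one test give one power, whatever the SD refers to.

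**Conclusion.** Both inconsistencies hold and should be fixed. The 60-per-arm label is the error; the total of 120 is sound as a count of paired infants if 0.5 of the mean is the SD of the change, or equivalently if the pre/post correlation is about 0.5 with that SD per measurement. On that basis the chance of missing a 15% change with methylxanthines is about 10% with 120 pairs, against 37% if 60 were taken as the number to measure.

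The more consequential part is physical therapy and cromolyn. With 120 pairs, the same SD and no true difference, power lies between 80.6% and 94.8% depending on a test and an alpha that the plan does not give. The stated 90% and 80% can both be right only under different conventions.

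**What to change.** In section 5.2, Aim 4:

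1. In the methylxanthines, physical therapy and cromolyn lines, replace the arm split with 120 infants, each with a paired pre- and post-treatment X7.
2. State that 0.5 of the mean is the SD of the within-infant change. Otherwise give the assumed pre/post correlation with its justification, and the power that follows.
3. For physical therapy and cromolyn, state whether the test is non-inferiority or equivalence and the per-side alpha, the same for both, and name that test in section 5.1. Then give both lines the one power from the 120-pair column of step 3.
4. If only 60 paired infants per therapy are intended, say so. Restate the methylxanthines power as about 63%, and take the other two from the 60-pair column.

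The cost is wording, possibly with a less favourable stated power once the convention and the SD are declared. Under items 1 to 3 the total of 120, the paired design and the paired test for the superiority lines do not change.

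### Physical therapy and cromolyn are sized on a 15% non-inferiority margin, but Section 5.1 states no criterion that uses the margin

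*Combined protocol and SAP*

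**What the plan says.** Section 5.2, Aim 4, sizes eight therapies. Six are sized to detect an improvement in X7. The other two, physical therapy and nebulized cromolyn sodium, are sized to show no important loss. For physical therapy, X7 "measurements will have no significant difference with a non-inferiority margin of 15% following this therapy we plan to recruit 120 (60 per arm) infants", with 90% power, 5% type I error and an SD of 0.5 of the mean. The cromolyn entry repeats the margin, SD and type I error, but there "we plan to recruit 120 infants (60 per arm) assuming power of 80" per cent.

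Section 4.2.4 (Aim 4 control) describes a within-infant comparison, "pairing the pre-treatment pulmonary function values (control) for an individual patient with the post-treatment values (intervention) for the same individual patient".

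Section 5.1 gives the paired t test for paired parametric data and the "Wilcoxon signed rank test for non-independent non-parametric data". It also lists unpaired tests, categorical tests, analysis of covariance and multiple regression. The significance threshold of p<0.05 is the only decision rule. The margin appears nowhere outside the two Aim 4 entries.

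**The concern.** Finding no significant difference and showing non-inferiority within a margin are different conclusions. The first can follow simply from imprecise data. The second requires the data to exclude a worsening as large as the margin. Section 5.2 joins the two in one phrase, and Section 5.1 supplies a criterion only for the first.

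An analyst who follows Section 5.1 literally would run a paired test of zero change and have no stated way to bring in the 15%. The choice of null value, one-sided level and scale of the margin would then be made after the data are in, although the abstract describes the aims and hypotheses as pre-specified. A non-significant result could also be reported as though it settled the question.

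The sizing hypothesis is itself unclear, because identical inputs are given two different powers.

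**Working it through.** **Inputs.** Margin 0.15, SD 0.5, both as shares of the mean (Section 5.2, Aim 4). N = 120. Type I error 5%, sidedness not stated. Pairing from Section 4.2.4. True change is taken as zero for power. X7 is negative and more negative is worse: Aim 3 expects, for example, an "absolute 50% difference (more negative) in term infants with MAS compared to term controls", and Aim 4 treats more positive as improvement.

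**Step 1: which SD is 0.5?** The plan does not say whether it belongs to single measurements or to the paired difference. The superiority entries help. Pairs needed at two-sided 5% and 90% power with SD of difference 0.5 are n = (0.5 × (1.960 + 1.282) / d)², then checked with the noncentral t:

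| Entry | d | Normal | t-based | Planned |
|---|---|---|---|---|
| Albuterol: "absolute 15% difference (more positive) following this therapy we plan to recruit 120 infants assuming power of 90" per cent | 0.15 | 117 | 119 | 120 |
| Furosemide: "absolute 20% difference (more positive) following this therapy we plan to recruit 70 infants assuming power of 90" per cent | 0.20 | 66 | 68 | 70 |
| Systemic steroids: "absolute 30% difference (more positive) following this therapy, we plan to recruit 30 infants assuming power of 90" per cent | 0.30 | 30 | 32 | 30 |

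The fit is close, so SD of difference = 0.5 is the central case. It equals a single-measurement SD of 0.5 with pre/post correlation r = 0.5, since SD of difference = 0.5 × √(2(1 − r)).

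**Step 2: reproduce the planned number.** Paired non-inferiority at one-sided 2.5% and 90% power uses the same formula with d = 0.15: 117 pairs (normal) or 119 (t). The 120 for physical therapy is reproduced as 120 infants, each measured before and after. At 80% power the same hypothesis needs 88 (normal) or 90 (t), so cromolyn's 120 is not reproduced. In power terms, 120 pairs give 90.3% at one-sided 2.5% and 94.8% at one-sided 5%; neither is 80%.

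**Step 3: what if non-significance were read as the answer?** With 120 pairs the standard error is 0.5/√120 = 0.0456. At a true worsening of 0.15 the noncentrality is 0.15/0.0456 = 3.29. The chance that a two-sided 5% paired t test is non-significant is 9.7% (noncentral t, 119 df). A test against a fixed margin would wrongly conclude non-inferiority 2.5% of the time at that point.

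The two criteria can also disagree on the same data. The critical t is 1.980, so changes within ±1.980 × 0.0456 = ±0.090 are non-significant, whereas non-inferiority needs a mean change above −0.15 + 0.090 = −0.060. An observed worsening of about 6% to 9% would show no significant difference and still fail the margin.

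**Step 4: sensitivity to correlation**, if 0.5 is the SD of single measurements (120 pairs):

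| r | SD of difference | Full-margin worsening missed |
|---|---|---|
| 0 | 0.707 | 36.5% |
| 0.5 | 0.500 | 9.7% |
| 0.8 | 0.316 | 0.07% |

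The r = 0 row is an extreme for repeat measurements in the same infant.

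**Step 5: power of a margin rule that needs no X7 units.** A 15% relative worsening means post = 1.15 × pre on average, so D = post − 1.15 × pre has mean zero at the margin. With mean X7 scaled to −1 and no true change, D has mean −1 + 1.15 = 0.15. Its SD is 0.5 × √(1 + 1.15² − 2 × 1.15 × r) = 0.541 at r = 0.5. With 120 pairs the power at one-sided 2.5% is 85.3%, and 90% needs 139 pairs. At r = 0 and r = 0.8 the power is 57.1% and 99.7%.

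In simulation (normal data, n = 60 and 120, r = 0, 0.5 and 0.8), this rule's error at a true 15% worsening was 2.5% throughout. Treating 0.15 times the observed pre-treatment mean as a fixed margin gave 3.4% to 3.7%.

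**The case against.** A paired t test can be run against a shifted null, and a confidence interval comes with it, so the tools in Section 5.1 could serve. That is true, but the section states neither the shift nor an interval rule. The covariate models do not fill the gap, as they too bring in no margin.

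A reader might infer that the plan equates p≥0.05 with non-inferiority. It does not say so. It only offers no other criterion, and the 9.7% is conditional on that reading.

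A reader might take the 60 per arm literally and conclude that power is badly short; 60 pairs would give 62.8%. The documents do not support leaning on this. The methylxanthines entry, a superiority comparison with the same total of 120, also says 60 per arm, while albuterol has the same inputs and mentions no arms. The phrase looks like a wording slip over 120 pairs, though it still conflicts with the pairing in Section 4.2.4.

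It is also tempting to assign non-inferiority to physical therapy and equivalence to cromolyn, because 120 pairs give 80.6% for equivalence at 2.5% per side. But 120 pairs also give 89.5% for equivalence at 5% per side, and the 80% may be a typing error. The text does not settle it.

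Finally, one cannot simply demand a margin in X7 units. Section 3.3 says the technique has not been used before in newborns, and no mean X7 is given. This objection stands, and it is why the fix leads with a relative margin.

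**Conclusion.** The point holds. For two of the eight Aim 4 therapies, the hypothesis that sets the sample size has no matching decision rule in the analysis plan. On the best-supported reading (120 pairs, SD of the paired difference 0.5), using non-significance as the answer would miss a full-margin worsening 9.7% of the time, against 2.5% for a margin test. That gap is real but modest, and its size depends on the unstated correlation. The mismatch between 90% and 80% power at identical inputs does not depend on that assumption.

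The finding is not that 120 is too few: 120 pairs reproduce for non-inferiority with a fixed margin. It should be corrected before analysis, but it concerns two therapy questions in the fourth aim of an observational study.

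**What to change.** **Section 5.1**, for these two therapies:
- Analyse paired pre- and post-treatment X7. Conclude non-inferiority only if the lower limit of the two-sided 95% confidence interval for the mean of (post − 1.15 × pre), with mean X7 negative, exceeds 0.
- Use a margin in X7 units only if one can be justified and fixed before the analysis. Do not treat 0.15 times the observed mean as fixed.
- State that p≥0.05 is not evidence of no effect. If equivalence is intended for either therapy, say so and give its level.

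**Section 5.2**:
- Replace the no-significant-difference wording with the chosen hypothesis, true change assumed zero.
- State the one-sided level and whether 0.5 is the SD of the paired difference.
- Reconcile 60 per arm, here and under methylxanthines, with the pairing in Section 4.2.4.
- Reconcile the 90% and 80%, and restate the power.

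**Cost**: a few sentences and no new data, but a somewhat lower stated power. The relative rule gives about 85% with 120 pairs at r = 0.5; keeping 90% would take 139 pairs, 19 more per therapy. With 120 pairs and an SD of difference of 0.5, 90% holds only if the margin is fixed in X7 units.
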